## 5.2 Dose Modification

### 5.2.1 General Dose Adjustment Note

The severity of AEs will be graded according to the NCI CTCAE v4.03. Reasons for dose modifications or delays, the supportive measures taken, and the outcome will be documented in the patient's chart and recorded in the CRF.

- Any toxicity that meets the definition of DLT during the DLT observation period will be considered as DLT for purposes of dose escalation and MTD determination.
- For any concomitant conditions already apparent at baseline, the dose modifications will apply according to the corresponding shift in toxicity grade, if the investigator feels it is appropriate. For example, if a patient has Grade 1 asthenia at baseline that increases to Grade 2 during treatment, this will be considered a shift of one grade and treated as Grade 1 toxicity for dose-modification purposes.
- For toxicities that are considered by the investigator to be unlikely to develop into serious or life-threatening events, treatment will be continued at the same dose. In addition, no dose reductions or interruptions will be required for anemia (non-hemolytic) because it can be satisfactorily managed, unless serious (Grade  $\geq 3$ ) hemorrhage is present.
- To recover from acute toxicity, unless otherwise indicated, the treatment can be interrupted for up to 14 days. If a treatment delay longer than 14 days is required, the patient should be discontinued from the study drug. Continuation/resumption of fruquintinib treatment after an interruption of more than 14 days must be discussed with the medical monitor or his or her designee.
- Where several toxicities with different grades or severity occur at the same time, the dose modifications should be according to the highest grade observed.

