## 5.2.2 Dose Modification Guidance

### 5.2.2.1 Dose Modification Sequence by Starting Dose and for General Hematologic and Non-Hematologic Toxicity

Dose reduction guidelines by starting dose and for haematologic and non-haematologic toxicities other than PPE, proteinuria, hypertension, decreased platelet count, hemorrhage, and liver function impairment are shown in [Table 7](#) and [Table 8](#). In principle, treatment should be held until AE/toxicity resolves or improves to  $\leq$ Grade 1. If a Grade 3 toxicity is expected to be manageable and reversible with a dose reduction, treatment should be held until toxicity resolves to  $\leq$ Grade 1. Patients with Grade 3 non-haematologic toxicity that does not resolve to  $\leq$ Grade 1 within 2 weeks should permanently discontinue the study drug.

Patients starting at 5 mg QD are allowed to have two dose reductions: one reduction from 5 mg QD to 4 mg QD, and if not tolerated, then a second reduction from 4 mg QD to 3 mg QD. Patients starting at 3 mg QD are allowed to have 1 dose reduction (ie, from 3 mg QD to 2 mg QD). The lowest dose level permitted in the study is 2 mg (see [Table 7](#)).

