**Table 8 Dose Modification for Hematologic and Non-Hematologic Toxicity**

NCI CTCAE v4.03 Toxicity Grading	Action
Grade 1 or 2 a	None
Grade 3 b	Interrupt the dose until the toxicity resolved to ≤Grade 1 or baseline level within 14 days, then reduce the dose to lower a dose level
Grade 4	Discontinue treatment permanently

a Should any arterial thrombosis occur, the treatment should be terminated.

b Including Grade 3 diarrhea and stomatitis, etc. that are ineffectively treated by drug therapies, but excluding Grade 3 menstrual cycle extension.

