### 5.2.2.2 Dose Modification and Treatment Suggestions for Selected Identified Risks

The dose modification and treatment suggestions for specific identified risks are provided in [Table 9](#) (PPE), [Table 10](#) (proteinuria), [Table 11](#) (hypertension), [Table 12](#) (decreased platelet count), [Table 13](#) (hemorrhage at any site), and [Table 14](#) (abnormal liver function).

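### For Grade 3 non-hemolytic anemia without Grade 3 or higher hemorrhage, Section 5.2.1 requires no dose change while Table 8 directs interruption and reduction, and neither is given precedence

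*Protocol*

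**What the plan says.** Three places in Protocol Section 5.2 bear on anemia.

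- **Section 5.2.1, general note.** "no dose reductions or interruptions will be required for anemia (non-hemolytic) because it can be satisfactorily managed". The sentence goes on "because it can be satisfactorily managed, unless serious" (Grade 3 or higher) hemorrhage is present. The exemption covers non-hemolytic anemia only, lapses with such hemorrhage, and has no ceiling on the anemia grade. It speaks of reductions and interruptions and does not mention permanent discontinuation.
- **Section 5.2.2.1.** Tables 7 and 8 are given "for haematologic and non-haematologic toxicities other than PPE, proteinuria, hypertension, decreased platelet count, hemorrhage, and liver function impairment". Anemia is not in that list.
- **Table 8.** The action at Grade 3 is "Interrupt the dose until the toxicity resolved to ≤Grade 1 or baseline level within 14 days, then reduce the dose" by a level; at Grade 4 it is "Discontinue treatment permanently". Footnote b to the Grade 3 row makes one exclusion, "but excluding Grade 3 menstrual cycle extension". Neither footnote mentions anemia or refers back to Section 5.2.1.

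Section 5.2.2.2 begins "The dose modification and treatment suggestions for specific identified risks are provided in" and lists Tables 9 to 14. None of them covers anemia, so it has no table of its own.

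**The concern.** A site managing a Grade 3 fall in hemoglobin can find two answers within a few pages. One says that no interruption or reduction is needed; the other says to hold the drug and restart lower. If sites choose differently, similar patients receive different doses for reasons unrelated to their condition.

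The SAP reports the quantities this would touch: relative dose intensity and the numbers with interruptions and reductions (Section 15.1), and TEAEs leading to interruption or reduction (Section 17.2.2). There is also a possible knock-on. Section 5.2.1 says a patient who needs a delay of more than 14 days should come off study drug, with any resumption discussed with the medical monitor. A slow recovery under the Table 8 route could therefore end treatment, whereas under the exemption no hold would have been required.

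**Working it through.** The plan gives no figure to reproduce, so the check applies both rules to the same event. Grades follow SAP Appendix 6: hemoglobin below 8.0 g/dL is Grade 3, from 8.0 to below 10.0 g/dL is Grade 2, and no laboratory Grade 4 is listed.

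| Event | Section 5.2.1 | Section 5.2.2.1 with Table 8 | Result |
|---|---|---|---|
| Grade 1 or 2, non-hemolytic, no Grade 3+ hemorrhage | No change required | No action | Agree |
| Grade 3, non-hemolytic, no Grade 3+ hemorrhage | No reduction or interruption required | Interrupt, then reduce | **Conflict** |
| Grade 3, with Grade 3+ hemorrhage | Exemption lapses | Table 8 for the anemia, Table 13 for the bleed | No conflict from the exemption |
| Grade 3, hemolytic | Exemption does not apply | Interrupt, then reduce | No conflict |
| Grade 4, non-hemolytic, no Grade 3+ hemorrhage | Silent on permanent discontinuation | Stop permanently | Unclear |

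**Effect of the baseline grade-shift bullet.** For a condition already present at baseline, Section 5.2.1 lets the investigator act on the change in grade. Baseline Grade 2 moving to Grade 3 is a shift of 3 − 2 = 1, handled as Grade 1. Baseline Grade 1 moving to Grade 3 is a shift of 3 − 1 = 2, handled as Grade 2. Table 8 asks for nothing at either, so the two rules agree if the investigator uses the provision. Because it is discretionary, it narrows the conflict without closing it. For a patient with no anemia at baseline it gives no relief.

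**Size per patient.** With the planned cohort sizes, one patient is 1/40 = 2.5% of Cohort B or C and 1/15 = 6.7% of Cohort D or E in any count of dose modifications.

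**Size for relative dose intensity.** SAP Section 15.3 uses 5 × 21/28 = 3.75 mg/day as the reference. Table 7 takes a 5 mg patient to 4 mg at the first reduction. A full cycle at 4 mg gives 4 × 21/28 = 3.00 mg/day, and 3.00/3.75 = 80%. Each full cycle after such a reduction thus contributes 80% rather than 100%, before counting days missed during the hold. The patient-level value depends on when the reduction occurs.

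**Frequency.** Protocol Table 3 does not list anemia among the identified risks, and no other part of the documents gives a rate. The number of affected patients cannot be estimated.

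**The case against.** The best reply is that Section 5.2.1 is a specific rule and Table 8 a generic one. Section 5.2.1 names non-hemolytic anemia and gives a reason and a limit; Table 8 never mentions it. The six toxicities set aside in Section 5.2.2.1 are exactly those with their own tables (9 to 14), so the list may only route readers to those tables rather than enumerate everything exempt from Table 8. Other bullets in Section 5.2.1, such as the grade-shift provision, also modify table actions without being repeated there. Section 3.1.1 points readers to Section 5.2 as a whole for dose modification, and Section 5.2.2.1 calls its content guidelines.

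That reading is plausible, but the text does not establish it. No sentence gives Section 5.2.1 precedence, and its heading marks it as the general note. Table 8 does carry an exclusion of its own in a footnote, so a reader could fairly expect an anemia exclusion to appear there too. It might also be said that an action that is not required is not forbidden, so a site that interrupts breaches neither text. Whether the action is mandatory is still left open.

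Several stronger readings are tempting, and the documents do not support them:

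- **All anemia is exempt.** It is not; hemolytic anemia and anemia with Grade 3 or higher hemorrhage fall outside the exemption.
- **The rules are flatly opposed at Grade 4.** Section 5.2.1 does not mention permanent discontinuation, and SAP Appendix 6 has no laboratory Grade 4, so a Grade 4 would have to come from the investigator's adverse event grading.
- **A patient entering at the 9.0 g/dL limit shows how easily the conflict arises.** That patient is already Grade 2, and the grade-shift provision may remove the conflict.
- **PFS is affected because patients taken off drug leave scan follow-up.** At Grade 3, Table 8 calls for interruption and reduction, not immediate removal. Section 6.4 keeps patients who stop without progression in efficacy follow-up, Appendix A footnote 17 has available assessments recorded until progression for Cohorts B to E, and SAP Table 1 does not censor at drug discontinuation.

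**Conclusion.** The inconsistency is real and narrow. It is literal for Grade 3 non-hemolytic anemia without Grade 3 or higher hemorrhage, mainly in patients without anemia at baseline or whose investigator does not apply the grade-shift provision. At Grade 4 the position is unclear, not contradictory. The reported quantities at risk are relative dose intensity and the counts of TEAEs leading to interruption or reduction. Whether handling would in fact differ between sites is a possibility created by the wording, not something the documents show.

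Severity is low to moderate: the frequency is unknown, but the wording concerns dosing instructions, a single patient is visible in the 15-patient cohorts, and correction is cheap. The conclusion assumes that anemia counts as a hematologic toxicity in Section 5.2.2.1 and that no separate site instruction already settles precedence. It takes no view on which rule is clinically right.

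**What to change.** Reconcile Section 5.2.1, the list in Section 5.2.2.1, and Table 8 with its footnotes, so that a single rule for anemia by grade reads the same in each. The wording should state:

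- whether Table 8 applies to Grade 3 non-hemolytic anemia without Grade 3 or higher hemorrhage;
- what happens at Grade 4;
- how the rule relates to the baseline grade-shift bullet.

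The sponsor's clinical team decides the content. The cost is a few lines in the next amendment or an administrative letter to sites, with no change to sample size, assessments or analysis.

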**Table 9 Dose Modification for PPE**

AE Grading Standard	Dose Adjustment	Treatment Suggestions
Grade 1: numb, paresthesia, dysesthesia, erythema, painless edema, desquamation, thicken skin and hand and foot discomfort which does not affect the normal activities; without any pain	None.	Active supportive treatment can be adopted to relieve the symptoms; for example, moisturizing skin cream, lotion, or hydrophilic urea ointment can be used.
Grade 2: erythema with pain accompanied by hand and foot swelling and /or discomfort, which affects normal activities	The drug could be interrupted; and no dose reduction if the AE recovers to Grade 1 or baseline level within 14 days.	Active supportive treatment can be adopted to relieve the symptoms; for example, moisturizing skin cream, lotion, or hydrophilic urea ointment can be used.
Grade 3: wet desquamation, ulcer, blister or severe hand and foot pain or severe discomfort, which affects work or normal activities.	The drug can be interrupted; the drug should be reduced to a lower dose level if the AE recovers to Grade 1 or baseline level within 14 days.	Active supportive treatment can be adopted to relieve the symptoms; Should the same AE occur for 3 times or still occurs after 2 times of dose reduction, the drug should be terminated.

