**Table 10 Dose Modification for Proteinuriaa**

AE Grading Standard	Dose Adjustment	Treatment Suggestions
Grade 1: Proteinuria 1+ by urinalysis;  24-hour urine protein quantitation <1.0 g	None	Follow up at scheduled study visits.
Grade 2: Proteinuria 2+ by the urinalysis;  24-hour urine protein quantitation is between 1.0 to <2.0 g	None	Provide supportive treatment and increase the frequency of urine monitor to once a week; consult nephrologist if necessary.
Grade 2: Proteinuria 2+ or above by urinalysis;  24-hour urine protein quantitation is between 2.0 to <3.5 g (excluding 3.5 g)	The drug can be interrupted and then reduced to lower if the AE recovers to Grade 1 or baseline level within 14 days.	Provide supportive treatment and increase the frequency of urine monitor to once a week; consult nephrologist if necessary.
Grade 3: 24-hour urine protein quantitation ≥3.5 g	The drug can be interrupted and then reduced to lower dose level if AE recovers to Grade 1 or baseline level within 14 days.	Provide supportive treatment and increase the frequency of urine monitor to once or twice a week; consult nephrologist if necessary. Should the same AE occur for 3 times or still occurs after 2 times of dose reduction, the drug should be terminated.

a: If protein ≥ 2+ on urinalysis during the study, a 24-hour urine test should be conducted within 1 week, and dose modification will be done by the result of 24-hour urine protein quantitation.

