**Table 11 Dose Modification for Hypertension**

AE Grading and Definitions	Dose adjustment	Treatment Suggestions
Grade 1: prehypertension  (systolic BP 120-139 mmHg or diastolic BP 80-89 mmHg)	None	Follow up as planned schedule
Grade 2: SBP 140-159 mmHg or DBP of 90-99 mmHg; or DBP symptomatic increase >20 mmHg	None	Treatment objective: lower the blood pressure to <140/90 mmHg (or <130/80 mmHg in patients with chronic renal disease and/or diabetes).  Refer to Appendix I .
Grade 3: SBP $\geq$ 160 mmHg or DBP $\geq$ 100mmHg; or more than one drug or more intensive therapy are used	Interrupted once Grade3 hypertension lasting more than 7 days after using or adjusting antihypertensive drug; Should the BP of the patient recover to Grade 1 or the baseline level, one time of dose reduction shall be made.	Treatment objective: lower the blood pressure to <140/90 mmHg (or <130/80 mmHg in patients with chronic renal disease and/or diabetes).  Refer to Appendix I .
Grade 4: Life threatening (eg, malignant hypertension, temporary or permanent neurological deficits and hypertensive crisis)	The drug should be terminated.	Emergent medical treatment.

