**Table 12 Dose Adjustment for Decreased Platelet Count**

AE Grading	Dose Adjustment	Treatment Suggestions
Grade 1: Platelet count <LLN - 75,000/ mm  ; <LLN - 75.0 × 10  /L	None	Perform follow up visit as scheduled.
Grade 2: Platelet count <75,000- 50,000/mm  ; <75.0 - 50.0 × 10  /L	Be interrupted and continue the drug treatment with the same dose should the AE recovers to Grade 1 or baseline level within 7 days.	Hematology test should be monitored every 2-3 days; active treatment for platelet elevation is recommended.
	Be interrupted and then reduced to the lower dose level should the AE recovers to Grade 1 or baseline level within 7-14 days.	Hematology test should be monitored every 2-3 days; active treatment for platelet elevation is recommended.
Grade 3: Platelet count <50,000 - 25,000/mm  ; <50.0 - 25.0 × 10  /L	Be interrupted and reduced to the lower dose level should the AE recovered to Grade 1 or baseline level within 14 days.	Hematology test should be monitored every 2-3 days; active treatment (platelet transfusion) to elevate the platelet count is recommended.  Hematology examination should be performed once every week in the follow up visit.
Grade 4: Platelet count <25,000/mm  ; <25.0 × 10  /L	The study drug should be terminated permanently.	Hematology test should be performed once daily until the AE recovers to Grade 2 or a lower grade; platelet transfusion or other active treatment should be provided

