**Table 13 Dose Adjustment for Hemorrhage at any Site**

AE Grading	Dose Adjustment	Treatment Suggestions
Grade 1	None	Perform follow up visit as scheduled.
Grade 2	The drug can be interrupted and then reduced to the lower dose level should the AE recovered to Grade 1 or baseline level within 14 days.	Provide Active treatment b
Grade 3 or abovea	The study drug should be terminated permanently.	Emergent medical intervention b

a Refer to [Appendix J](#) for clinical management of severe or serious hemorrhage.

b The investigator should closely monitor patients receiving anti-platelet and/or anti-thrombotic drugs during study drug treatment and make a timely decision on whether to continue or stop such drugs in patients that report Grade ≥2 hemorrhagic events at any site, based on an individual assessment of the risk-benefit balance (See Section 5.3.1 Concomitant therapies).

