**Table 14 Dose Adjustment for Abnormal Liver Function**

AE Grading a	Dose Adjustment	Treatment Suggestions
Grade 1	None.	Perform follow-up visit as scheduled.
Grade 2 or 3 (Liver function is abnormal but the biochemical criteria for Hy's Law b are not met)	
 
1. Drug interruption can be considered;
 
2. The dose should be reduced to the lower dose level if the AE recovers to Grade 1 or baseline within 14 days.
 
	Provide supportive care and increase the frequency of liver function monitoring to 1-2 times a week.
Grade 2 or 3 (Liver function is abnormal and the biochemical criteria for Hy's Law b are met)	The study drug should be terminated immediately.	Provide supportive care and increase the frequency of liver function monitoring to 2-3 times a week. Urgent medical intervention indicated.
Grade 4	The study drug should be terminated.	Urgent medical intervention indicated.

a Including increasing of ALT, AST, and total bilirubin, whether or not the biochemical criteria for Hy's Law have been met.

b Hy's Law is an increase in serum AST or ALT  $\geq 3 \times$  ULN together with total bilirubin  $\geq 2 \times$  ULN, and no other reason can be found to explain the biochemical changes, for example, new or worsening hepatobiliary metastases, elevated serum ALP indicating cholestasis, viral hepatitis, another suspect drug, or any other specific cause of severe hepatocellular injury. The elevation in transaminases must precede or be coincident with (ie, on the same day as) the elevation in total bilirubin, but there is no specified timeframe within which the elevations in transaminases and total bilirubin must occur. See Section 7.1.2 for special reporting requirements and Appendix H for additional information regarding Hy's Law.

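### The concurrent-toxicity rule in Protocol 5.2.1 goes by highest grade, but grade does not rank the dose actions, so early Grade 3 hypertension could override a Grade 2 platelet hold

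*Protocol*

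**What the plan says.** The last bullet of Protocol 5.2.1 is the only sentence that decides between dose-modification tables when toxicities coincide: "Where several toxicities with different grades or severity occur at the same time, the dose modifications should be according to the highest grade observed".

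The tables it has to arbitrate between include:

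- **Table 11, Grade 3 hypertension:** "Interrupted once Grade3 hypertension lasting more than 7 days after using or adjusting antihypertensive drug". No dose action is listed before that point. Grade 3 can also be reached on treatment intensity alone, through use of more than one drug or more intensive therapy.
- **Table 12, Grade 2 platelets, recovery within 7 days:** "Be interrupted and continue the drug treatment with the same dose".
- **Table 12, Grade 2 platelets, recovery in 7 to 14 days:** "Be interrupted and then reduced to the lower dose level".

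Other Grade 2 entries with an action are softer. Examples are Table 9 for PPE ("The drug could be interrupted; and no dose reduction") and Table 14 for liver abnormality not meeting Hy's Law ("Drug interruption can be considered").

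**The concern.** A highest-grade rule assumes that strictness of action rises with grade across all the tables. It does not. Grade 2 entries range from no action (Table 8, the first Grade 2 row of Table 10, Table 11), through interruption (Table 12), to termination (Table 14 when Hy's Law criteria are met). A Grade 3 entry can carry no immediate action (Table 11 in the first 7 days).

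The rule can therefore point to the less protective instruction. A site applying the bullet literally could keep dosing a patient whose platelets call for a hold, while another site following Table 12 would stop.

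Both toxicities are identified risks of this drug in Table 3: hypertension 55.4% and platelet decrease 19.4%. Hemorrhage is listed there at 40.7%, and Appendix J names thrombocytopenia as a possible contributor to bleeding. What is at stake is individual safety management over a few days, and consistency across approximately 12 sites. No endpoint or analysis depends on it.

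**Working it through.** The plan gives no figure to reproduce here. The check is to set the tables side by side, apply the bullet literally, and then size the result.

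**1. Which Grade 2 entries conflict with early Grade 3 hypertension?** Setting the Hy's Law row aside, five specific-risk tables give some action at Grade 2:

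| Table | Grade 2 toxicity | Wording on interruption | Direct instruction? |
|---|---|---|---|
| 9 | PPE | "The drug could be interrupted; and no dose reduction" | No, optional |
| 10 | Proteinuria, 2.0 to <3.5 g | "The drug can be interrupted and then reduced to lower if the AE recovers" | No, optional |
| 12 | Platelets, both rows | "Be interrupted and continue the drug treatment with the same dose" / "Be interrupted and then reduced to the lower dose level" | Yes |
| 13 | Hemorrhage | "The drug can be interrupted and then reduced to the lower dose level" | No, optional |
| 14 | Liver, Hy's Law not met | "Drug interruption can be considered" | No, optional |

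One of the five is worded as a direct instruction, so the clear conflict is limited to platelets.

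**2. Apply the bullet.** Take a patient with Grade 3 hypertension, 7 days or less since an antihypertensive was started or adjusted, and Grade 2 platelets.

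- The highest grade is 3, so Table 11 governs. Its trigger has not been met, so it calls for no hold.
- Table 12 alone would call for a hold at once.
- The literal rule therefore gives the less restrictive result.

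**3. Does other text rescue the case?**

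- The general hold in 5.2.2.1 belongs to guidance introduced for toxicities other than a list that names both hypertension and decreased platelets. An investigator could borrow the principle, but it is not a rule for this pair.
- The fourth bullet of 5.2.1 permits an interruption of up to 14 days. It does not require one.
- The third bullet of 5.2.1 allows judgment, but in the direction of continuing at the same dose.
- Section 5.2.2.2 introduces the tables as suggestions, which softens Table 12 but does not say which table prevails.
- Hy's Law cases have a separate mandatory stop (7.1.3.2, Appendix H), as do arterial thromboembolic events (5.3.1). For those the bullet is only inconsistent wording. Grade 2 platelets have no equivalent backstop.

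**4. Size per patient.** Inputs: 5 mg daily for 21 days of each 28-day cycle (5.1.6, Table 7), and a Table 11 trigger of more than 7 days. All window days are assumed to be dosing days.

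- Cycle dose: 21 × 5 mg = 105 mg.
- Platelet fall found on day 3 of the window: days 3 to 7 = 5 doses; 5 × 5 mg = 25 mg; 25/105 = 23.8%.
- Both toxicities starting together: days 1 to 7 = 7 doses; 7 × 5 mg = 35 mg; 35/105 = 33.3%.

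These are maxima for a single window. They would be exceeded if each antihypertensive adjustment restarts the 7 days, which Table 11 leaves open. Frequency cannot be calculated: the documents give neither a Grade 2 platelet rate nor a co-occurrence rate.

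**The case against.** The strongest reply is that nothing actually competes. The bullet can be read as choosing between dose modifications. In the first 7 days Table 11 offers none, so Table 12 supplies the only one and applies. Table 11 prints an explicit no-change entry for Grades 1 and 2 but not for Grade 3, so treating its silence as an order to keep dosing goes too far. This reading is reasonable and many investigators would adopt it. It is not the only reading, and no text requires it.

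Second, the wording of Table 12 is loose. Its Grade 2 entries have no subject or modal verb, and even the Grade 3 entries for PPE and proteinuria say only that the drug can be interrupted, so the difference between mandatory and optional may be accidental. That is fair as a caution. But Table 12 opens its Grade 3 entry with the same words as its Grade 2 entries, which favors reading the Grade 2 hold as mandatory too.

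Third, sites could already differ over isolated Grade 2 platelets because of the third bullet of 5.2.1. Harm is also limited: Table 12 sets hematology every 2 to 3 days at Grade 2, and a fall to Grade 3 would tie the grades and bring in Table 12's own Grade 3 hold. Both points stand and keep the matter minor. They do not justify a rule that can select the weaker instruction. The percentages describe doses in constructed cases and do not measure harm.

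**Conclusion.** The concern holds, as a minor safety-instruction point. Highest grade does not order the actions in the tables, and for Grade 3 hypertension of 7 days or less with concurrent Grade 2 platelets, a literal reading puts the Table 12 hold in doubt. The exposure is up to 5 doses (24% of a 5 mg cycle) in the day-3 example and up to 7 doses (33%) with same-day onset.

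This rests on reading Table 12's Grade 2 entries as instructions, on a literal reading of the bullet, and on the window falling on dosing days. Confidence is medium, because investigator discretion could avoid the problem at most sites and the frequency is unknown.

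**What to change.** In the last bullet of 5.2.1, replace the highest-grade criterion with: *according to the most restrictive action specified by the applicable tables for any of the concurrent toxicities*. No table needs to change. Holds that a table words as optional are meant to stay optional, and the clarification can say so.

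The cost is one sentence, at the next amendment or in a clarification letter to sites. The downside is an occasional extra interruption, with no data or analysis cost. Because the third bullet of 5.2.1 still allows judgment, the change will reduce differences between sites but not remove them all.
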